#### **5.2.3. Prior/Concurrent Clinical Study Experience**

- Concurrently participating in another clinical study, at any time during the study period, in which the participant has been or will be exposed to an investigational or a non-investigational intervention (drug/invasive medical device). Refer to [Definition of Terms](#) for the definition of invasive medical device. EXC#15

#### **5.2.4. Other Exclusion Criteria**

- History of chronic alcohol consumption and/or drug abuse as deemed by the investigator to render the potential participant unable/unlikely to provide accurate safety reports or comply with study procedures. EXC#16
- Bedridden participants. EXC#17
- Planned move during the study conduct that prohibits participation until study end. EXC#18
- Participation of any study personnel or their immediate dependents, family, or household members. EXC#19

### **5.3. Caregiver support**

Study participants may decide to assign a caregiver to help them fulfilling the study procedures. Please refer to definition of terms for the definition of a caregiver.

A caregiver can be appointed by the participant at any time during the study, when the participant feels it's necessary. Each caregiver should receive the caregiver information letter before providing support to the study participant. Ideally, a single caregiver should be appointed by the participant but, in some situations, it may happen that several caregivers will support a study participant throughout the conduct of the study. This should be recorded in the source documents.

Caregivers may help the study participants with performing some practical study procedures such as receiving or making phone calls to study staff, planning study visits, transcribing responses to diaries, performing the nasal swab (only for study participants in China), transportation to and from the study site, etc. However, at no time, the caregiver should evaluate the participant's health status while answering diaries or make

decisions on behalf of the participant. At the time of recruitment, the study staff should inform the participant of the possibility to appoint a caregiver. Then, at each study visit with the exception of the end of study visits, the site staff should check with the participant if he/she wishes to appoint a caregiver or if there were or will be changes in caregiver.

#### **5.4. Lifestyle considerations**

Not applicable.

#### **5.5. Screen failures**

A screen failure occurs when a participant who has consented to participate in the clinical study is not enrolled into the study. A minimal set of screen failure information is required to ensure transparent reporting of screen failure participants to meet the CONSORT publishing requirements and to respond to queries from regulatory authorities. Minimal information includes demography, screen failure details, eligibility criteria, information from any previous trials with the same IP, and any SAE.

Individuals who do not meet the criteria for participation in this study (screen failure) may not be rescreened.

Screen number assigned to screen failure participants cannot be reassigned to another participants.

For the overseas arm, if the subjects are positive to any pathogens tested during screening, they will not participate in this study.

#### **5.6. Criteria for temporarily delaying enrollment and/or administration of study intervention**

Study vaccine administration may be postponed within the permitted timeframe for study vaccination until transient circumstances cited below are resolved:

- Acute disease and/or fever at the time of vaccination. Fever is defined as a temperature  $\geq 37.3^{\circ}\text{C}$  by axillary route. Oral temperature = axillary temperature +  $0.2^{\circ}\text{C}$ .
- Participants with a minor illness (such as mild diarrhoea, mild upper respiratory infection) without fever may be vaccinated at the discretion of the investigator.
- In case of administration of inactivated and subunit influenza vaccines or Coronavirus Disease 2019 (COVID-19) vaccines: Postponement of study vaccine administration within given protocol timelines to allow respect of the 14 day-interval between flu/COVID-19 vaccination and study vaccine administration.

## 6. STUDY INTERVENTIONS AND CONCOMITANT THERAPY

The definition of study intervention is provided in the table of definitions.

### 6.1. Study interventions administered

**Table 9 Study Interventions Administered**

Study intervention Name:	RSVPreF3 OA Investigational Vaccine		Placebo
Study intervention formulation	RSVPreF3 (120 µg)	AS01 E : QS-21* (25 µg), MPL (25 µg), liposomes; Water for injections	NaCl (0.9%); Water for injections
Presentation	Powder for suspension for injection (vial)	Suspension for suspension for injection (vial)	Solution for injection (syringe)
Type	Investigational		Comparator
Product category	Biologics		Combination product
Route of Administration	Intramuscular		Intramuscular
Administration site			
Location	Deltoid		Deltoid
Directionality	Upper		Upper
Laterality	Non-dominant		Non-dominant
Number of doses to be Administered	1		1
Volume to be administered**	0.5 mL		At least 0.5 mL***
Packaging and labelling	Refer to Pharmacy Manual for details		Refer to Pharmacy Manual for details
Manufacturer	GSK		GSK

AS01E = Adjuvant System 01; QS-21 = *Quillaja saponaria* Molina, fraction 21; MPL = monophosphoryl lipid A

\* Licensed by GSK from Antigenics Inc, a wholly owned subsidiary of Agenus Inc., a Delaware, USA corporation.

\*\* Refer to the Pharmacy Manual for the volume after reconstitution. 0.5 mL of the reconstituted RSVPreF3 OA vaccine is to be injected.

\*\*\* The volume of the saline pre-filled syringe may be between 0.6 and 0.8 mL. The full volume is to be injected.

Study participants must be observed closely for at least 30 minutes after the administration of the study interventions. Appropriate medical treatment must be readily available during the observation period in case of anaphylaxis, syncope.

#### 6.1.1. Medical Devices

- The GSK manufactured medical devices (or devices manufactured for GSK by a third party) provided for use in this study are placebo prefilled syringes. Other medical devices (not manufactured by or for GSK) provided for use in this study are thermometer for body temperature measurement, ruler for skin reaction

measurement, materials for study intervention administration, syringes, biological sample collection kits and oximeters.

- Instructions for medical device use are provided in Laboratory Manual and Pharmacy Manual.
- All device deficiencies (including malfunction, use error and inadequate labeling) shall be documented and reported by the investigator throughout the clinical investigation (see Sections 8.4.6 and 10.4) and appropriately managed by GSK.

## **6.2. Preparation, handling, storage, and accountability**

- The investigator or designee must confirm appropriate conditions (e.g., temperature) have been maintained during transit for all study intervention received, and any discrepancies are reported and resolved before use of the study intervention.
- Only participants enrolled in the study may receive study intervention, and only authorized site staff may supply, prepare, or administer study intervention.
- All study intervention must be stored in a secure, environmentally controlled, and monitored (manual or automated) area in accordance with the labelled storage conditions with access limited to the investigator and authorized site staff.
- The investigator, or authorized site staff is responsible for study intervention accountability, reconciliation, and record maintenance (i.e., receipt, reconciliation, and final disposition records).
- Further guidance and information for the final disposition of unused study interventions are provided in the pharmacy manual.

## **6.3. Assignment to study intervention**

All participants will be centrally assigned to the study intervention using an IVRS/IWRS. Before the study is initiated, the telephone number and call-in directions for the IVRS and/or the log-in information and directions for the IWRS will be provided to each site.

Study intervention will be dispensed at the study visits as summarized in the SoA (Section 1.3).

Returned study intervention should not be re-dispensed to the participants.

Participants who withdraw from the study will not be replaced.

## **6.4. Blinding**

Data from study participants in China will be collected in an observer-blind manner. The participant, the site and sponsor personnel involved in the clinical evaluation of the participants are blinded while unblinded study personnel may be aware of the treatment assignment. To do so, vaccine will be prepared and administered by qualified study personnel (unblinded) who will not participate in data collection, evaluation or review of

any study endpoint (i.e., reactogenicity, safety, ARI surveillance). The study is open-labelled for participants enrolled in the overseas arm.

Refer to pharmacy manual regarding details of the tasks that can be performed by the unblinded study personnel. The unblinded study personnel are allowed to transcribe source data (as detailed in Section 10.1.9) into the eCRF without interpretation or generation of data.

The laboratory in charge of the sample testing will be blinded to the intervention assignment in study participants in China. Codes will be used to link the participant and study (without any link to the intervention attributed to the participant) to each sample. There will be no link between the study intervention groups and the identity of the participant.

The study will be conducted in an observer-blind manner (for study participants in China) from study start and will remain blinded up to study end. The results from the primary analyses (Day 31) may be shared with the principal investigators. The individual data listings and participant treatment assignments will not be provided to the investigators until after the conclusion of the study.

Note that limited members of GSK central study team (CSL, Statistician, Safety Representative, etc.) may be fully/partially unblinded to the study intervention assignment at the time of Day 31 analysis.

#### **6.4.1. Emergency unblinding**

This is a partial blind study in which the qualified personnel are blinded to study intervention for participants in China. The IVRS/IWRS will be programmed with blind-breaking instructions. In case of an emergency, the investigator has the sole responsibility for determining if unblinding of a participants' intervention assignment is warranted. Participant safety must always be the first consideration in making such a determination. If the investigator decides that unblinding is warranted, the investigator may, at the investigator's discretion, contact GSK to discuss the situation prior to unblinding a participant's intervention assignment unless this could delay emergency treatment for the participant. If a participant's intervention assignment is unblinded, GSK must be notified within 24 hours of this occurrence. The date and reason for the unblinding must be recorded.

If the investigator is unable to access IVRS/IWRS, they can contact the GSK helpdesk based on the information provided in the pharmacy manual.

A physician other than the investigator (e.g., an emergency room physician) or participant/participant's caregiver or family member may also request emergency access to the participant's study intervention information as per participant card.

A participant may continue in the study if that participant's intervention assignment is unblinded. The primary reason for discontinuation (the event or condition which led to the unblinding) will be recorded in the eCRF.

GSK's Global Safety staff may unblind the intervention assignment for any participant with an SAE. If the SAE requires that an expedited regulatory report be sent to 1 or more regulatory agencies, a copy of the report, identifying the participant's intervention assignment, may be sent to investigators in accordance with local regulations and/or GSK policy.

## **6.5. Study intervention compliance**

Participants will receive the study intervention, under medical supervision, directly from the investigator or designee. The date and time of the dose administered in the clinic will be recorded in the source documents.

A record of the quantity of study intervention dispensed to and administered by each participant must be maintained and reconciled with study intervention and compliance records. Intervention start and stop dates, including dates for intervention delays and/or dose reductions will also be recorded.

## **6.6. Dose modification**

Not applicable.

## **6.7. Continued access to study intervention after the end of the study**

During the study conclusion visit, the investigator will ask each participant if they are interested in participating a long-term evaluation study. If a participant is not interested in joining the long-term evaluation study the reason for refusal will be documented, when available, in the participant's eCRF.

## **6.8. Treatment of overdose**

Not applicable.

## **6.9. Prior and concomitant therapy**

Any medication or vaccine (including over-the-counter or prescription medicines, recreational drugs, and/or herbal supplements) or other specific categories of interest that the participant is receiving at the time of enrollment or receives during the study must be recorded along with:

- Reason for use
- Dates of administration including start and end dates
- Dosage information including dose and frequency

The medical monitor should be contacted if there are any questions regarding concomitant or prior therapy.

At each study visit/contact, the investigator or delegate should question the participant about any medications/products taken and vaccinations received by the participant.

The following concomitant medication(s)/product(s)/vaccine(s) must be recorded in the eCRF:

- All concomitant medication, except vitamins and dietary supplements, administered during the 30-day period following the administration of study vaccine.
- All concomitant vaccination during the entire study period.
- All concomitant medication including vaccines/products which may explain/cause/be used to treat an SAE/pIMD as defined in Sections 8.4.1 and 8.4.3. These must also be recorded on the Expedited AE report.
- For all AF AESIs (including serious and non-serious), concomitant drugs which could be associated with development or worsening of AF must be reported in the AF follow-up questionnaire.
- Any antipyretic administered in the period starting 6 hours before vaccination and ending 12 hours after vaccination need to be recorded on the eCRF. An anti-pyretic is considered prophylactic when given in the absence of fever, to prevent fever from occurring.
- All concomitant medications taken for the treatment of an ARI (including prescribed drugs [e.g. antibiotics] and self-treatment) or for an ARI-related complication (Study participants in China only).
- All concomitant medications including vaccines/products leading to discontinuation of the study intervention or an elimination from the analysis (refer to Section 5.2.2 for details).

The Local Clinical Lead should be contacted if there are any questions regarding concomitant or prior therapy.

## **7. DISCONTINUATION OF STUDY INTERVENTION AND PARTICIPANT DISCONTINUATION/WITHDRAWAL**

### **7.1. Discontinuation of study intervention**

Not applicable.

### **7.2. Participant discontinuation/withdrawal from the study**

A participant may withdraw from the study at any time at the participant's own request for any reason (or without providing any reason).

A participant may be withdrawn at any time at the discretion of the investigator for safety, behavioral, or compliance reasons.

Investigators will attempt to contact participants who do not return for scheduled visits or follow-up.

The participant will be permanently discontinued from the study intervention and the study at that time.

All data and samples collected up to and including the date of withdrawal of/last contact with the participant will be included in the study analyses. If the participant withdraws consent for disclosure of future information, the sponsor may retain and continue to use any data collected before such a withdrawal of consent.

If a participant withdraws from the study, the participant may request destruction of any samples taken and not tested, and the investigator must document this in the site study records.

The primary reason for participant discontinuation/ withdrawal from the study will be documented in the eCRF based on the list below:

Reasons	Additional items/Sub-reasons
AE	AEs requiring expedited reporting to GSK Unsolicited AE* Solicited AE*
Lost to follow-up	Subject Relocated Subject was Incarcerated Other, specify Unknown
Physician Decision	Specify
Protocol Deviation	Specify
Site Terminated by Sponsor	
Study Terminated by Sponsor	
Withdrawal by Participant	Burden of Procedure Participant Relocated Pursue Alternative Treatment COVID-19 Pandemic Other
Other	Specify
Death	

\*For study participants in China only

Study participants in China who are withdrawn from the study because of AEs/SAEs must be clearly distinguished from participants who are withdrawn for other reasons. Investigator will follow participants who are withdrawn from the study due to an AE/SAE until the event is resolved (see Section [10.3.5.5](#)).

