Treatment	Population	Endpoint (Variable)	Intercurrent events (ICEs)		Population level summary
			Description	Handling strategy	
RSVPreF3 OA investigational vaccine at Day 1.	China older adult with ≥ 60 YOA	Occurrence of RT-PCR-confirmed RSV A and/or B-associated ARI and LRTD, according to the case definition. In study participants in China with RT-PCR-confirmed RSV A and/or B associated ARI and LRTD cases: 
 Duration of episodes. Reported symptoms/signs. ARI/LRTD severity. Frailty status. 	Taking prohibited medication /vaccine or intercurrent medical condition during study duration.	All the data collected for the variable of interest are used regardless of whether the intercurrent event occurs (treatment policy strategy).	The percentage of participants by group who report each of the endpoints except duration of episodes. Group mean of duration of episodes

RSV=Respiratory syncytial virus; YOA=Years of age.

The estimands for secondary ARI surveillance is to characterize the RSV-confirmed ARI and LRTD cases in Chinese older adult.

ESTIMANDS FOR SAFETY

The clinical question of interest is to evaluate the safety and reactogenicity after RSVPreF3 OA investigational vaccine administration in vaccinated Chinese older adults.

The estimands for safety evaluation are described in [Table 4](#):

Table 4 Study estimand - secondary safety objective

[figure not shown]
Attributes					
Treatment	Population	Endpoint (Variable)	Intercurrent events (ICEs)		Population level summary
			Description	Handling strategy	

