RSVPreF3 OA investigational vaccine at Day 1.	Chinese and overseas OA with ≥60 YOA	For RSV OA group (China) and Placebo group (China): 
 • Occurrence of each solicited administration site event with onset within 7 days after study intervention administration (i.e., the day of study intervention administration and 6 subsequent days). • Occurrence of each solicited systemic event with onset within 7 days after study intervention administration (i.e., the day of study intervention administration and 6 subsequent days). • Occurrence of unsolicited AEs within 30 days after study intervention administration (i.e., the day of study intervention administration and 29 subsequent days). • Occurrence of SAEs after study intervention administration (Day 1) up to 6 months after study intervention. • Occurrence of pIMDs after study intervention administration (Day 1) up to 6 months after study intervention. • Occurrence of SAEs related to study intervention after study intervention administration (Day 1) up to study end. • Occurrence of pIMDs related to study intervention after study intervention administration (Day 1) up to study end. • Occurrence of any fatal SAEs after study intervention administration (Day 1) up to study end. 	Taking prohibited medication /vaccine or intercurrent medical condition during respective duration.	All the data collected for the variable of interest are used regardless of whether the intercurrent event occurs (treatment policy strategy).	The percentage of participants by group who report each of the endpoints.

Attributes					
Treatment	Population	Endpoint (Variable)	Intercurrent events (ICEs)		Population level summary
			Description	Handling strategy	
		For RSV OA group (Overseas): 
 • Occurrence of SAEs after study intervention administration (Day 1) up to study end (Month 6). • Occurrence of pIMDs after study intervention administration (Day 1) up to study end (Month 6). • Occurrence of SAEs related to study intervention after study intervention administration (Day 1) up to study end (Month 6). • Occurrence of pIMDs related to study intervention after study intervention administration (Day 1) up to study end (Month 6). • Occurrence of any fatal SAEs after study intervention administration (Day 1) up to study end (Month 6). 			

AE=Adverse event; pIMD=Potential immune-mediated disease; RSV=Respiratory syncytial virus; SAE=Serious adverse event; YOA=Years of age.

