3.1.3. Elimination from Per-Protocol Set

A participant will be excluded from the populations for analysis under the following conditions:

- For codes 800, 900, 1030, 1060, 1070, 1080, 1090 and 2010: participants will be eliminated for all visits.
- For codes 1040, 2040 and 2050: participants will be eliminated from a specific visit (at which the condition is met) onwards.
- For codes 2020 2090, 2100, 2120: participants will be eliminated at the specific visit at which the condition is met.

Table 6 List of elimination codes

Code	Condition under which the code is used	Visit / Contact (timepoints) where the code is checked	Visit from when it is applicable	Applicable for analysis set/endpoint
800	Fraudulent data	All	All	Enrolled Set, ES, PPS
900	Invalid informed consent	All	All	Enrolled Set, ES, PPS
1030	Study intervention not administered at all	Visit 1	All	ES, PPS
1040	Administration of concomitant vaccine(s) forbidden in the protocol (as defined in Section 5.2.2 of protocol)	All	From the specific visit the condition is met	PPS
1060	Randomization code was broken (Chinese participants only)	All	All	PPS
1070	Vaccine administration not according to protocol: 
 • Participant was vaccinated with the correct vaccine but containing a lower volume • Wrong replacement or study vaccine administered (not compatible with the vaccine regimen associated to the treatment number) • Route of the study vaccine is not intramuscular • Wrong reconstitution of administered vaccine 	Visit 1	All	PPS
1080	
 • Vaccine administration after a temperature deviation • Vaccine administered despite a Good Manufacturing Practices (GMP) no-go temperature deviation 	Visit 1	All	PPS
1090	Vaccine administration after expiration	Visit 1	All	PPS
2010	Protocol deviation linked to inclusion/exclusion criteria	All	All	PPS
2020	All Pre-dose results are missing	Visit 1	At the specific visit the condition is met	PPS

Code	Condition under which the code is used	Visit / Contact (timepoints) where the code is checked	Visit from when it is applicable	Applicable for analysis set/endpoint
2040	Administration of any medication forbidden by the protocol (as defined in Section 5.2.2 of protocol)	All	From the specific visit the condition is met.	PPS

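### Protocol 7.2 lets a site withdraw an already vaccinated participant for non-compliance or a protocol deviation, so new safety and RSV illness events are no longer actively sought; a short retention rule would prevent this.

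*Protocol*

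**What the plan says.** **Protocol 4.1 and 7.1.** Each participant gets a single dose at Visit 1. The section on stopping study intervention is marked as not applicable.

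**Protocol 7.2.** "A participant may be withdrawn at any time at the discretion of the investigator for safety, behavioral, or compliance reasons". The effect is stated as "The participant will be permanently discontinued from the study intervention and the study at that time". The table of primary reasons includes "Protocol Deviation". The data kept for analysis are "All data and samples collected up to and including the date of withdrawal of/last contact with the participant". There is one retention rule: "Investigator will follow participants who are withdrawn from the study due to an AE/SAE until the event is resolved".

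**Protocol 8.4.1 and 8.4.3.** After participation ends, investigators need not actively look for AEs or SAEs. A later SAE that they happen to learn of goes in the medical records, and the sponsor must be told only if it is considered related. SAEs and AESIs already reported are followed to an outcome.

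**SAP 1.1, Tables 3 and 4.** For ARI the intercurrent events are "Taking prohibited medication /vaccine or intercurrent medical condition during study duration". The safety table names the same two kinds of event. Both tables apply this strategy: "All the data collected for the variable of interest are used regardless of whether the intercurrent event occurs (treatment policy strategy").

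**Protocol 9.2.1 and SAP 3.1.3.** The stated consequence of prohibited therapy is possible elimination from the Per-Protocol Set (PPS). Code 1040, for example, covers "Administration of concomitant vaccine(s) forbidden in the protocol (as defined in Section 5.2.2 of protocol").

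**SAP 4.3.2 and 4.3.3.** ARI and safety are analysed on the Exposed Set.

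**The concern.** After Visit 1 there is no treatment left to stop, so withdrawal for non-compliance or a deviation ends only observation. Nothing is gained for the primary analysis, because the PPS codes already decide whether a deviator's serum counts.

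What is lost is new information: later SAEs, pIMDs and deaths, RSV-confirmed ARI and LRTD in China, and the Month 6 serum. The participant stays in the Exposed Set denominator with little chance of a further recorded event, so the percentages can only move down. The loss may also not be random. Most of what stays prohibited throughout the study under Protocol 5.2.2 is immune-modifying drugs, immunoglobulins and blood products, and people who come to need these may differ in their risk of a later SAE or pIMD.

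The estimand is affected in one case. If the deviation is itself the use of a prohibited medication or vaccine, the SAP wants the data after that event, and the protocol lets a site stop collecting them because of it.

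**Working it through.** **1. Does the text allow the loss?**

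| Question | Source | Answer |
|---|---|---|
| Can a vaccinated participant be withdrawn for compliance? | Protocol 7.2 | Yes, at any time |
| Is a deviation a coded reason? | Protocol 7.2 | Yes |
| Are new events sought afterwards? | Protocol 8.4.1 | No obligation |
| Are known SAEs/AESIs, and AE/SAE withdrawals, still followed? | Protocol 7.2, 8.4.3 | Yes |
| Is withdrawal required for prohibited therapy? | Protocol 9.2.1 | No; PPS elimination is possible |
| Does any text ask sites to keep a vaccinated deviator in follow-up? | Both documents | None found |

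**2. Overlap with the SAP's intercurrent events.** Non-compliance, protocol deviation and withdrawal are not intercurrent events in Tables 3 and 4. The overlap is limited to prohibited medication or vaccine. For vaccines it is narrow: EXC#11 restricts other vaccines only from 30 days before to 30 days after the dose, so a registered vaccine at Month 2 is not a deviation under it.

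**3. Does the PPS already handle deviators?** Yes. Under SAP 3.1.3, codes 1040 and 2040 remove a participant from the visit concerned onwards, 2090 removes a single visit, and 2010 removes all visits.

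**4. The plan's own figure.** Attrition enters only the power table (Protocol Table 21, SAP Table 7). With 10% loss, n = 800 × 0.9 = 720 Overseas and 1200 × 0.9 = 1080 China vaccine.
- GMT: noncentral t with noncentrality [log10(1.5) − log10(GMR)] / [0.45 × √(1/720 + 1/1080)], one-sided 0.025.
- SRR: normal approximation with the Miettinen-Nurminen restricted null variance, margin 10 points.
- Overall power: product of the four individual powers.

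| Scenario | Stated | Recomputed |
|---|---|---|
| 1 | 90.5% | 90.5% |
| 2 | 98.2% | 98.3% |
| 3 | 99.6% | 99.6% |
| 4 | 96.0% | 96.0% |

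The figures reproduce with 10% loss already included. Loss before Day 31 would have to exceed the planned 10% to matter: at an assumed 15% or 20%, scenario 1 falls to 88.9% or 87.0%, and the other scenarios stay at or above 93.4%.

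**5. How many participants?** Planned attrition is 10% of 1200, 600 and 800, which is 120, 60 and 80 (total 260). The investigator-initiated share is not given; 10-30% is assumed.
- RSV vaccine recipients: 10-30% of (120 + 80 = 200) = 20-60.
- All participants, placebo included: 10-30% of 260 = 26-78.
- As a fraction of those enrolled: 0.10 × 10% = 1% to 0.30 × 10% = 3%.

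**6. How many events missed?** Assume a constant event rate over 180 days, the same rate in those withdrawn, and no capture after withdrawal. Share missed = w × (fraction of follow-up remaining), where w is the fraction withdrawn.

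| w | Spread evenly (w × 0.5) | Around Day 31 (w × 150/180) | Just after the dose (w × 1) |
|---|---|---|---|
| 1% | 0.5% | 0.8% | 1.0% |
| 3% | 1.5% | 2.5% | 3.0% |
| 10% (all planned attrition; outer bound) | 5.0% | 8.3% | 10.0% |

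At 2.5% missed, a true six-month percentage of 4% would be observed as 4% × 0.975 = 3.9%. If those withdrawn have a higher event rate than the rest, the missed share rises roughly in proportion.

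**The case against.** The strongest reply is that the documents do not contradict each other. The SAP says that data collected are used; it makes no promise that participants will be followed. Withdrawal is permissive, and the documents' own route for prohibited therapy is to record it (Protocol 6.9) and consider PPS elimination (Protocol 9.2.1). All of this stands. A reader might infer that the SAP requires follow-up which the protocol forbids, or that every compliance withdrawal collides with an SAP intercurrent event. The text supports neither reading.

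A reader might also infer that all follow-up ends. It does not, because AE/SAE withdrawals and SAEs/AESIs already reported are still followed. A new disease that leads to a prohibited drug may itself be the reportable event. The gap is later events that nobody seeks, or that are learned of but judged unrelated.

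The AF finding in the earlier efficacy study (Protocol 8.4.4.2: 10 v 4 events, 7 v 1 serious) invites a stronger argument than it can bear. That imbalance arose within 30 days of vaccination, and none was seen for serious AF over six months. It supports the point only for withdrawals before Day 30.

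In China, clinical staff are blinded, so differential withdrawal between the arms is not shown. The SAP tabulates safety follow-up time (4.3.3) and withdrawal reasons (6.1.1), so a shortfall would be visible. Visibility does not recover the data, and the ARI and safety percentages carry no stated adjustment for follow-up time.

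Finally, sites need some discretion, for instance over disruptive conduct. That is a fair reason to leave the behavioural ground alone.

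**Conclusion.** The point holds in a limited form. Protocol 7.2 allows a vaccinated participant to be taken out of the study for non-compliance or a deviation, after which new SAEs, pIMDs and RSV-confirmed ARI/LRTD are not actively sought. Where the deviation is prohibited product use, this can remove data that the treatment policy estimands would use. It is a gap that leaves the estimand exposed to site discretion, short of a contradiction between the documents.

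The probable size is small: 20-60 vaccine recipients, and about 0.8-2.5% of six-month events missed with withdrawal around Day 31. That rests on an assumed 10-30% investigator-initiated share of a 10% attrition figure set for power planning, a constant event rate, and the same risk in those withdrawn. None of these can be checked from the documents. The endpoints concerned are descriptive and secondary, and primary power is untouched. The change is worth making because it is cheap and withdrawing these participants brings no analytic benefit.

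**What to change.** In Protocol 7.2, state that once study intervention has been given, non-compliance, a protocol deviation or use of a prohibited medication or vaccine is not on its own a reason to end SAE/AESI follow-up, ARI surveillance (China) or serum sampling, as far as the participant agrees. Add that the PPS elimination codes decide the immunogenicity contribution. Restrict the "Protocol Deviation" withdrawal reason to the period before vaccination.

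Leave the safety and behavioural grounds, participant request, loss to follow-up, death and sponsor termination as they are.

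The cost is protocol wording, one eCRF option and a note to sites. The downside is that sites keep contacting a few less compliant participants. No visits are added, and the primary analysis is unchanged.
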